Appendix B: Imputation Rules for Missing Prior/Concomitant Medication Dates

Imputation rules for missing or partial medication start/stop dates are defined below:

1. Missing or partial medication start date:
 - a. If only DAY is missing, use the first day of the month.
 - b. If DAY and Month are both missing, use the first day of the year.
 - c. If DAY, Month and Year are all missing, use a date before the first dose date (in practical, use Jan. 01, 2000 to impute).
2. Missing or partial medication stop date:
 - a. If only DAY is missing, use the last day of the month.
 - b. If DAY and Month are both missing, use the last day of the year.
 - c. If DAY, Month and year are all missing, assign ‘continuing’ status to stop date (in practical, use Dec. 31, 2050 to impute).

In summary, the prior, concomitant, or post categorization of a medication is described below.

Table 12-2 Prior, Concomitant, and Post Categorization of a Medication

Medication Start Date	Medication Stop Date		
	< First Dose Date of Study Drug	≥ First Dose Date and ≤ End Date of TE Period	> End Date of TE Period
< First dose date of study drug	P	PC	PCA
≥ First dose date and ≤ End date of TE period	-	C	CA
> End date of TE period	-	-	A

P: Prior; C: Concomitant; A: Post

Imputation rules for missing and/or partial dates of non-pharmacological treatment/procedure will follow the same imputation rule.

Appendix D: Steps for Multiple Imputation

For the multiple imputation (MI) to be applied to the MMRM for the sensitivity analysis of the primary efficacy endpoint, the following steps will be followed:

Imputation distribution

The imputation distribution for the missing absolute change from baseline in ppFEV₁ at visit t will be a normal distribution. All subjects in the corresponding analysis set (e.g., FAS) will be classified into one of three categories based on the following rules:

- Non-missing category: Subjects who have a ppFEV₁ assessment at the last timepoint of the dependent variable. Given the primary analysis method, this corresponds to the subjects who have a non-missing absolute change from baseline in ppFEV₁ at Week 24.
- Missing category 1: Subjects with missing absolute change from baseline in ppFEV₁ at the last timepoint of the dependent variable (Week 24), who discontinued treatment because of adverse events, noncompliance with study drug, death, or physician decision, or because the subject refused further dosing or required prohibited medication.
- Missing category 2: Subjects with missing absolute change from baseline in ppFEV₁ at the last timepoint of the dependent variable (Week 24), who completed the protocol-specified treatment or discontinued treatment for any reason not listed in Category 1.

Imputation algorithm

We will use the following algorithm that relates the mean of the missing absolute change from baseline in ppFEV₁ at visit t to the missing categories defined above. The algorithm will be implemented within each treatment group as follows:

- Missing category 1: randomly draw a sample from the normal distribution (μ_{25}, σ^2) , where μ_{25} is the 25th percentile of the non-missing absolute changes from baseline in ppFEV₁ at visit t and σ^2 the sample variance estimated using the non-missing absolute changes at visit t .
- Missing category 2: randomly draw a sample from the normal distribution (μ, σ^2) , where μ is the mean of the non-missing absolute changes from baseline in ppFEV₁ at visit t and σ^2 is the sample variance estimated using the non-missing absolute changes at visit t .

Analysis model

The complete MI method is described below:

- Form an “imputed dataset” by imputing missing values at each visit for those subjects who have a missing value at the visit and have all subsequent values missing. The appropriate normal distribution specified in the algorithm above will be used for each such subject, based on their category.
- Repeat this process K ($K=20$) times to form K imputed datasets.
- Fit the same MMRM model as the one used for primary analysis to each imputed dataset to estimate the absolute change at Week 4.
- Combine the results from the analyses of K imputed datasets using the SAS procedure MIANALYZE to derive the MI estimator.

Let θ be the true treatment difference. Denote by $\tilde{\theta}_k$ the estimate of θ from the k^{th} imputed dataset, and the corresponding estimate of the variance is denoted by V_k . The MI estimator of θ , $\tilde{\theta}_{\text{MI}}$, is the average of the K individual estimates.

The estimated variance of $\tilde{\theta}_{\text{MI}}$ is a combination of the between- and within-imputation variability as follows: $V_{\text{MI}} = W + \left(1 + \frac{1}{K}\right)B$, where $W = \frac{1}{K} \sum_{k=1}^K V_k$ is the within-imputation variability and is $B = \frac{1}{K-1} \sum_{k=1}^K (\tilde{\theta}_k - \tilde{\theta}_{\text{MI}})^2$ is the between-imputation variance. The statistic $T = \frac{\tilde{\theta}_{\text{MI}} - \theta}{\sqrt{V_{\text{MI}}}}$ has an approximate t_V distribution⁷, where $V = (K - 1)\left(1 + \frac{W}{B}\right)^2$.

Appendix E: Imputation Rules for Missing AE dates

Imputation rules for missing or partial AE start date are defined below. If the imputed AE start date is before the study informed consent date, the AE start date will be imputed using the study informed consent date.

- **If only Day of AE start date is missing:**

- If the full (or partial) AE end date is NOT before the first dose date of the Treatment Period or AE end date is missing, then
 - if AE start year and month are equal to the month and year of first dose date of the Treatment Period, then impute the AE start day as the day of first dose date of the Treatment Period;
 - else impute the AE start day as 1.
- else impute the AE start day as 1.

Compare the imputed AE start date with TE period to determine whether the AE is pretreatment AE, TEAE or post-treatment AE.

- **If Day and Month of AE start date are missing:**

- If the full (or partial) AE end date is NOT before the first dose date of the Treatment Period or AE end date is missing, then
 - if AE start year is equal to the year of first dose date of the Treatment Period, then impute the AE start month and day as the month and day of first dose date of the Treatment Period;
 - else impute the AE start month as January and day as 1.
- else impute the AE start month as January and day as 1.

Compare the imputed AE start date with TE period to determine whether the AE is pretreatment AE, TEAE or post-treatment AE.

- **If Year of AE start date is missing:**

If the year of AE start is missing or AE start date is completely missing then query site and

- If the full (or partial) AE end date is NOT before the first dose date of the Treatment Period or AE end date is missing, then impute the AE start date as the first dose date of the Treatment Period;
- else impute the AE start date as the informed consent date.

Imputation rules for partial AE end date are defined below:

- Impute the AE end date as min (the last day of the month, end of study participation) if day is missing, or min (Dec, end of study participation) if month is missing.
 - For the IA purpose, if the end of study date is missing, then the IA data cutoff date will be used instead in the imputation

Appendix F: Criteria for Threshold Analysis

Table 12-3 Threshold Analysis Criteria for Laboratory Tests (as applicable)

Parameter	Threshold Analysis	Comments
Clinical Chemistry (LFT)		
ALT	>ULN - ≤3xULN >3x - ≤5xULN >5x - ≤8xULN >8x - ≤20.0xULN >20.0xULN	FDA DILI Guidance Jul 2009.
AST	>ULN - ≤3xULN >3x - ≤5xULN >5x - ≤8xULN >8x - ≤20.0xULN >20.0xULN	FDA DILI Guidance Jul 2009.
ALT or AST	(ALT>ULN - ≤ 3xULN) or (AST>ULN - ≤3xULN) (ALT>3x - ≤5xULN) or (AST>3x - ≤5xULN) (ALT>5x - ≤8xULN) or (AST>5x - ≤8xULN) (ALT>8x - ≤20xULN) or (AST>8x - ≤20xULN) ALT>20xULN or AST>20xULN	FDA DILI Guidance
Alkaline Phosphatase	>ULN - ≤1.5xULN >1.5 - ≤2.5xULN >2.5 - ≤5.0xULN >5.0 - ≤20.0xULN >20.0xULN	FDA DILI Guidance Jul 2009.
Total Bilirubin	>ULN - ≤1.5xULN >1.5 - ≤2xULN >2 - ≤3xULN >3 - ≤10xULN >10xULN	FDA DILI Guidance Jul 2009.
Direct Bilirubin	>ULN - ≤1.5xULN >1.5 - ≤2xULN >2 - ≤3xULN >3 - ≤10xULN >10xULN	FDA DILI Guidance Jul 2009.
ALT and Total Bilirubin	ALT>3xULN and TBILI>2xULN	FDA DILI Guidance Jul 2009.
AST and Total Bilirubin	AST>3xULN and TBILI>2xULN	FDA DILI Guidance Jul 2009.
(ALT or AST) and Total Bilirubin	(ALT>3xULN or AST>3xULN) and TBILI>2xULN	FDA DILI Guidance Jul 2009.

Table 12-3 Threshold Analysis Criteria for Laboratory Tests (as applicable)

Parameter	Threshold Analysis	Comments
GGT	>ULN - ≤2.5xULN >2.5 - ≤5.0xULN >5.0 - ≤20.0xULN >20.0xULN	CTCAE grade 1-4
Clinical Chemistry (NON-LFT)		
Albumin	<LLN - ≥30 g/L <30 - ≥20 g/L <20 g/L	CTCAE grade 1-3
Amylase	>1x - ≤1.5xULN >1.5x - ≤2xULN >2x - ≤5xULN >5xULN	Criteria based upon CTCAE
Creatinine	>ULN - ≤1.5xULN >1.5 - ≤3.0xULN >3.0 - ≤6.0xULN >6.0xULN	CTCAE grades 1-4
Lipase	>ULN - ≤1.5xULN >1.5x - ≤2xULN >2x - ≤5xULN >5xULN	Criteria based upon CTCAE
Total protein	<LLN >ULN	No CTCAE
Creatine kinase	>ULN - ≤2.5xULN >2.5 - ≤5xULN >5 - ≤10xULN >10xULN	CTCAE grades 1-4
Hematology		
Hemoglobin	Hgb decreased (anemia) <LLN - ≥100 g/L <100 - ≥80 g/L <80 g/L	CTCAE grade 1-3
	Hgb increased >ULN - ≤20 g/L above ULN >20 g/L above ULN - ≤40 g/L above ULN >40 g/L above ULN	CTCAE grade 1-3
Platelets	Platelet decreased <LLN - ≥75.0 x 10e9 /L <75.0 - ≥50.0 x 10e9 /L <50.0 - ≥25.0 x 10e9 /L <25.0 x 10e9 /L	CTCAE grade 1-4
	Platelet increased >ULN	No CTCAE available
Reticulocytes/Erythrocytes (%)	<LLN >ULN	No CTCAE

Table 12-3 Threshold Analysis Criteria for Laboratory Tests (as applicable)

Parameter	Threshold Analysis	Comments
Coagulation		
Activated partial thromboplastin time (PTT)	>ULN - $\leq 1.5 \times \text{ULN}$ >1.5 - $\leq 2.5 \times \text{ULN}$ >2.5xULN	CTCAE grade 1-3
Prothrombin time (PT) International Normalized Ratio (INR)	>ULN - $\leq 1.5 \times \text{ULN}$ >1.5 - $\leq 2.5 \times \text{ULN}$ >2.5 x ULN	CTCAE grade 1-3

Table 12-4 Threshold Analysis Criteria for ECGs

Parameter	Threshold Analysis	Comments
HR	Bradycardia <50 bpm <45 bpm Decrease from baseline ≥ 10 bpm Decrease from baseline ≥ 20 bpm <50 bpm and decrease from baseline ≥ 10 bpm <50 bpm and decrease from baseline ≥ 20 bpm	Per HV grade 2, 3, plus shift change
	Tachycardia >100 bpm >115 bpm >130 bpm Increase from baseline ≥ 10 bpm Increase from baseline ≥ 20 bpm >100 bpm and increase from baseline ≥ 10 bpm >100 bpm and increase from baseline ≥ 20 bpm	Per HV grade 1, 2, 3, plus shift change
PR	≥ 240 ms ≥ 300 ms ≥ 200 ms and increase from baseline ≥ 40 ms ≥ 200 ms and increase from baseline ≥ 100 ms	
	QRS >110 ms >160 ms Increase from baseline ≥ 20 ms Increase from baseline ≥ 40 ms	
QTc	>450 to <500ms (Male) or >470 to <500ms (Female) ≥ 500 ms	To be applied to any kind of QT correction formula.
	Increase from baseline Increase from baseline >10 ms Increase from baseline >20 ms Increase from baseline >40 ms Increase from baseline >60 ms	

Table 12-5 Threshold Analysis Criteria for Vital Signs

Parameter	Threshold Analysis	Comments
Pulse Rate	Same as above in ECG category	
SBP increased	>140 mmHg >160 mmHg >10 mmHg increase from baseline >20 mmHg increase from baseline >140 mmHg & >10 mmHg increase from baseline >140 mmHg & >20 mmHg increase from baseline >160 mmHg & >10 mmHg increase from baseline >160 mmHg & >20 mmHg increase from baseline	809/770 analyses
SBP decrease	<90 mmHg <80 mmHg >10 mmHg decrease from baseline >20 mmHg decrease from baseline <90 mmHg and >10 mmHg decrease from baseline <90 mmHg and >20 mmHg decrease from baseline <80 mmHg and >10 mmHg decrease from baseline <80 mmHg and >20 mmHg decrease from baseline	Per HV grade 1, 3, plus shift change
DBP increased	>90 mmHg >100 mmHg >5 mmHg increase from baseline >10 mmHg increase from baseline >90 mmHg and >5 mmHg increase from baseline >90 mmHg and >10 mmHg increase from baseline >100 mmHg and >5 mmHg increase from baseline >100 mmHg and >10 mmHg increase from baseline	
DBP decreased	<60 mmHg <45 mmHg >5 mmHg decrease from baseline >10 mmHg decrease from baseline <60 mmHg and >5 mmHg decrease from baseline <60 mmHg and >10 mmHg decrease from baseline <45 mmHg and >5 mmHg decrease from baseline <45 mmHg and >10 mmHg decrease from baseline	
Weight	Weight gain ≥5 % increase from baseline ≥10 % increase from baseline ≥ 20% increase from baseline Weight loss ≥5 % decrease from baseline ≥10 % decrease from baseline ≥ 20% decrease from baseline	CTCAE grade 1-3 CTCAE grade 1-3

Table 12-6 Threshold Analysis Criteria for Laboratory Tests (for labeling purpose)

Parameter	Threshold Analysis	Comments
Clinical Chemistry (LFT)		
ALT or AST	>3xULN >5xULN >8xULN	For labeling purpose

Appendix G: Adverse Events of Special Interest

Table 12-7 MedDRA Preferred Terms for Event of Special Interest	
Adverse event of special interest	MedDRA preferred terms
Elevated transaminase	Alanine aminotransferase abnormal, Alanine aminotransferase increased, Aspartate aminotransferase abnormal, Aspartate aminotransferase increased, Transaminases abnormal, Transaminases increased, Liver function test abnormal, Liver function test increased, Hypertransaminasaemia, Hepatic enzyme abnormal, Hepatic enzyme increased
Rash	Rash, Rash erythematous, Rash macular, Rash maculo-papular, Rash maculovesicular, Rash vesicular, Rash pruritic, Rash follicular, Rash pustular, Rash generalized, Nodular rash, Drug eruption, Fixed eruption, Generalised erythema, Urticaria, Urticaria popular, Urticaria vesiculosa, Rash morbilliform, Rash popular, Rash papulosquamous, Rash rubelliform, Rash scarlatiniform , Drug hypersensitivity, Type IV hypersensitivity reaction, Dermatitis, Dermatitis atopic, Epidermolysis, Skin toxicity, Dermatitis allergic, Dermatitis exfoliative, Dermatitis exfoliative generalized, Erythema multiforme, Exfoliative rash, Mucocutaneous rash, Acute generalised exanthematous pustulosis, Cutaneous vasculitis, Urticarial vasculitis, Dermatitis bullous, Drug reaction with eosinophilia and systemic symptoms, Epidermal necrosis, Oculomucocutaneous syndrome, Skin exfoliation, Skin necrosis, Stevens-Johnson syndrome, Toxic epidermal necrolysis, Toxic skin eruption, Perioral dermatitis, Vasculitic rash

Note: the preferred terms listed in the table is based on the MedDRA version applicable at the time of finalization of the SAP. If the MedDRA version is upgraded at the time of the analysis, the corresponding preferred terms based on the upgraded version will be used in the analysis of adverse events of special interest.

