13.1.1.2 Clinically Significant Assessments

Study assessments including laboratory tests, ECGs, PEs, and vital signs will be assessed and those deemed to have clinically-significant worsening from baseline will be documented as an AE. When possible, a clinical diagnosis for the study assessment will be provided, rather than the

abnormal test result alone (e.g., urinary tract infection, anemia). In the absence of a diagnosis, the abnormal study assessment itself will be listed as the AE (e.g., bacteria in urine or decreased hemoglobin).

An abnormal study assessment is considered clinically significant if the subject has 1 or more of the following:

- Concomitant signs or symptoms related to the abnormal study assessment
- Further diagnostic testing or medical/surgical intervention
- A change in the dose of study drug or discontinuation from the study

Repeat testing to determine whether the result is abnormal, in the absence of any of the above criteria, does not necessarily meet clinically significant criteria. The determination of whether the study assessment results are clinically significant will be made by the investigator.

A laboratory value that is Grade 4 will not automatically be an SAE. A Grade 4 laboratory value will be an SAE if the subject's clinical status indicates a life-threatening AE.

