13.1.1.3 Documentation of Adverse Events

All AEs will be collected from the time the ICF is signed until the subject completes study participation, as defined in [Section 9.1.6](#).

All subjects will be queried, using nonleading questions, about the occurrence of AEs at each study visit. When possible, a constellation of signs and/or symptoms will be identified as 1 overall event or diagnosis. All AEs for enrolled subjects will be recorded in the CRF and source document. AEs for subjects who are screened but not subsequently enrolled in the study will be recorded only in the subject's source documents. The following data will be documented for each AE:

- Description of the event
- Classification of "serious" or "nonserious"
- Date of first occurrence and date of resolution (if applicable)
- Severity
- Causal relationship to study drug(s)
- Action taken
- Outcome
- Concomitant medication or other treatment given

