9.4.7 Supportive Safety Analysis

9.4.7.1 Adverse Events of Special Interest

For this study, elevated transaminase events and rash events, as determined by MedDRA preferred terms in [Appendix G](#), are considered as adverse events of special interest.

For treatment-emergent elevated transaminase events and rash events, the following categories will be summarized by treatment group:

- Subjects with events

[figure not shown]
- Subjects with events by maximum severity
- Subjects with events leading to treatment discontinuation
- Subjects with events leading to treatment interruption
- Subjects with serious events
- Subjects with related serious events
- Subjects with events leading to death
- Duration of events
- Time-to-onset of first event

In addition, for treatment-emergent rash events, these categories will be summarized for the following subgroups:

- Sex (male, female)
- Female subjects with concomitant hormonal therapy (Yes, No)

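### Transaminase elevations recorded only under a liver diagnosis are not counted in the elevated-transaminase AESI summary, so its serious, discontinuation, interruption and fatal rows may be understated

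*SAP*

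**What the plan says.** SAP 9.4.7.1 defines two AESIs by term list: "For this study, elevated transaminase events and rash events, as determined by MedDRA preferred terms in" Appendix G. No other selection rule is given. For each AESI it tabulates by arm the subjects with any event, by maximum severity, leading to discontinuation, leading to interruption, serious, related and serious, and fatal. Duration and time to first onset are added.

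The Appendix G row headed elevated transaminase holds four ALT and AST terms (each *abnormal* or *increased*), followed by "Transaminases abnormal, Transaminases increased, Liver function test abnormal, Liver function test increased, Hypertransaminasaemia, Hepatic enzyme abnormal, Hepatic enzyme increased". The rash row of the same table runs from simple rash terms through to diagnoses, for example "Stevens-Johnson syndrome, Toxic epidermal necrolysis, Toxic skin eruption".

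On what sites write down, Protocol 13.1.1.2 says: "When possible, a clinical diagnosis for the study assessment will be provided, rather than the", and the sentence goes on to name the abnormal result standing alone. It then adds: "In the absence of a diagnosis, the abnormal study assessment itself will be listed as the AE". Protocol 13.1.1.3 says: "When possible, a constellation of signs and/or symptoms will be identified as 1 overall event or diagnosis".

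SAP 10.1.4 and 10.1.4.1 apply the same AESI definition at the interim analysis. Table 10-1 of the SAP makes that analysis the second planned data monitoring committee (DMC) review.

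**The concern.** The two documents pull in different directions. The protocol steers sites, where they can, towards a diagnosis. The SAP then looks for this AESI only under test-result terms. A site that follows the preferred recording practice can therefore remove a case from the summary meant to count it.

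The loss may also be selective. Protocol 9.8.1 asks for a thorough search for causes once an interruption threshold is met. Protocol 13.1.2.2 asks that serious events be recorded under a recognised medical term or a diagnosis. Both make a diagnosis more likely for marked or serious cases than for a mild isolated ALT rise. That is plausible reasoning; the documents contain no data on it.

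What is at stake is how the table can be read. An AESI summary exists to give one pooled count of subjects per arm, with seriousness, action taken and outcome attached. Under the present list, a zero in the serious or fatal row could mean that there was no such case, or that the case was coded to a diagnosis. The DMC would face the same ambiguity at the interim. No efficacy analysis is touched.

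**Working it through.** The plan states no figure to reproduce here. The check is a count of terms, followed by tracing how a case moves from site record to table.

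**1. Term count (SAP Appendix G).** Elevated transaminase: 2 ALT + 2 AST + 2 transaminases + 2 liver function test + 1 hypertransaminasaemia + 2 hepatic enzyme = 11. Ten contain *abnormal* or *increased*; the eleventh is hypertransaminasaemia. Terms naming a liver diagnosis: 0. Terms naming jaundice or raised bilirubin: 0. The rash row has 48 terms, including severe diagnoses. The note under the table covers MedDRA version changes and does not widen the scope.

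**2. From site record to AESI table.**

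| How the elevation is recorded | Matches Appendix G? | In the AESI summary? |
|---|---|---|
| Test-result term only (no diagnosis available) | Yes | Yes |
| Test-result term and a separate diagnosis term | Yes, through the first | Yes |
| Diagnosis term only | No | In no row |
| Not reported as an adverse event | No | No, by design |

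Only the third line is a gap. It can occur because Protocol 13.1.1.2 and 13.1.1.3 favour the diagnosis when one is available.

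**3. Where a diagnosis-only case still appears.**

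| Output | Shows the case? | What it lacks |
|---|---|---|
| Treatment-emergent event tables by system organ class and preferred term: all, Grade 3/4, serious, discontinuation, interruption, fatal (SAP 9.4.1) | Yes, under its own term | Does not pool it with test-result terms into one subject count per arm |
| Listings of serious, fatal, Grade 3/4, interruption and discontinuation events (SAP 9.4.1) | Yes, case by case | No count |
| ALT/AST thresholds, the combined ALT/AST and bilirubin criterion, scatter plots (SAP 9.4.2, Appendix F) | Yes, if laboratory values were obtained | Seriousness, action taken, relatedness, event outcome |

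**4. Size.** Let N be the subjects in an arm whose transaminase elevation is reported as an adverse event in any form, and d the share recorded only under a diagnosis. Then

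AESI count = N × (1 − d), and the relative shortfall is d.

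The same relation holds for each row, with its own N and d. The documents give neither quantity, so d may lie anywhere from 0 (no effect) to 1 (a row that reads zero although cases occurred). The direction for a count row is fixed: it can be too low through this route, never too high. The direction for duration, time to onset and the difference between arms cannot be stated.

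**The case against.** The strongest reply is that the list matches its label. The SAP defines elevated transaminase events, not liver events in general. A raised transaminase is a laboratory finding with its own laboratory analysis, whereas rash is a clinical finding for which clinical terms are natural. This stands as far as the label goes: a reader should not fault the plan for lacking a liver AESI it never promised. It does not remove the gap, because a subject with a marked ALT rise recorded as hepatitis does have an elevated transaminase.

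The second reply is that the recording rule is conditional. It applies when possible and is aimed at reporting the test result alone, so recording both terms is not barred. Protocol 11.7.2 also says that clinically significant abnormal laboratory results are reported as adverse events. This stands. Cases can drop out; nothing says that they must.

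The third is that the serious, interruption and discontinuation rows can still fill. The rules in Protocol 9.8.1 are triggered largely by ALT and AST values. Interruption precedes confirmatory testing, and mandatory discontinuation applies when no persuasive other cause is found. Such cases may have no diagnosis to record and would keep a test-result term. Seriousness and severity are recorded for every event. So a reader who infers that these rows cannot work, or that the most serious cases will necessarily be missing, goes further than the documents allow.

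The fourth is that other outputs keep these cases in view, at the interim as well as at the end (SAP 10.1.4 and 10.1.4.1). This also stands and limits the importance of the point. What those outputs do not give is the pooled adverse event count that the AESI table is for.

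**Conclusion.** The point holds in a limited form. A transaminase elevation recorded only under a liver diagnosis matches none of the 11 terms and is absent from the whole elevated-transaminase AESI summary. Its serious, discontinuation, interruption and fatal rows may therefore be understated, in both the final and the interim package. This rests on two assumptions: that Appendix G is applied as written, and that at least some cases carry a diagnosis and no test-result term.

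Two stronger readings are not supported. One is that severe liver cases would be hidden from the report or from the DMC: they would appear in the general and serious event tables, the listings and, where values exist, the threshold tables. The other is a numerical size. Supposing that 1 to 3 of 10 affected subjects carry only a diagnosis gives a shortfall of 1/10 to 3/10, or 10% to 30%, but those case numbers are assumptions with no source in the documents.

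This is a gap in one descriptive safety summary (SAP 9.4 plans no safety testing). It is worth closing because closing it is cheap.

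**What to change.** Before unblinding, amend Appendix G so that the transaminase AESI has two levels:

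- an expanded row that adds hepatic diagnosis terms which include or imply transaminase elevation, chosen by the sponsor's safety group without sight of treatment codes;
- the present 11 laboratory-type terms, kept unchanged as a separate sub-row.

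Report all the SAP 9.4.7.1 categories for both. For the interim package to benefit, the change must be in place before the interim data lock; the final analysis can take it through a SAP addendum, a route the sponsor already uses.

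The cost is an edit to one appendix and a longer term list in one program, with no new data collection. The small downside is that a few hepatic events without transaminase elevation may enter the expanded row. The retained sub-row keeps those apart from the events that the plan counts now.
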